6.3.1. Study duration

The duration of the study for each participant is expected to be ~12 weeks for the run-in and treatment phases and additional 8 weeks for those participating in the free-use phase.

6.4. Study endpoints

6.4.1. Primary endpoints

1. The safety of Nerivio

The incidence of adverse events in general and by seriousness, severity and association to the device.

2. Treatment tolerability

The percent of subjects who fail to complete the study because of adverse events

6.4.2. Secondary endpoints

1. Pain relief at 2 hours post-treatment:

The proportion of participants achieving pain relief, defined as improvement from severe or moderate pain to mild or none, or improvement from mild pain to none, at 2 hours post-treatment in the test treatment, with no use of rescue medication

- 2. Pain-free at 2 hours post-treatment:
 - The proportion of participants achieving pain freedom, defined as improvement from mild, moderate, or severe pain to none, at 2 hours post-treatment in the test treatment, with no use of rescue medication
- 3. Disappearance of associated symptoms at 2 hours post-treatment
 - a. The proportion of participants reporting nausea at baseline and achieving absence of nausea at 2 hours post-treatment in the test treatment
 - b. The proportion of participants reporting phonophobia at baseline and achieving absence of phonophobia at 2 hours post-treatment in the test treatment
 - c. The proportion of participants reporting photophobia at baseline and achieving absence of photophobia at 2 hours post-treatment in the test treatment

6.4.3. Exploratory endpoints

1. Sustained pain relief at 24 hours post-treatment:

The proportion of participants achieving pain relief at 2 hours post-treatment in the test treatment, with no use of rescue medication and no relapse of headache pain within 24 hours

Nerivio TCH-004 Clinical Study Protocol (NCT04089761)

Doc ID: TEC0105

Revision #: 1.0

Page: 32 of 49

2. Sustained pain-free at 24 hours post-treatment:

The proportion of participants achieving pain freedom at 2 hours post-treatment in the test treatment, with no use of rescue medication and no relapse of headache pain within 24 hours

3. Functional disability at 2 hours post treatment

The proportion of participants who achieve improvement of at least one grade in functional disability in the test treatment at 2 hours post-treatment, with no use of rescue medication

4. Functional disability at 24 hours post treatment

The proportion of participants who achieve improvement of at least one grade in functional disability in the test treatment, with no use of rescue medication

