The individual intensity level identified during this visit will be recorded, and the participants will be asked to treat their migraine headaches with the device using the identified intensity. If the research staff recognizes that the participant cannot tolerate the feeling of the electrical stimulation, the participant may be withdrawn from the study.

During the training, participants will also be informed on the key elements which are critical for the successful conduct of the study:

- Treatments of attacks with Nerivio[™] should be performed as soon as possible
 after migraine headache or aura began and always within one hour of symptoms
 onset. Treatments of mild headaches are accepted.
- Avoid taking rescue medications within two hours post-treatment (2 hours from start of treatment), if possible.
- The treatment should be performed for at least 30 minutes (the recommended treatment duration is 45 minutes).

Phase 2 –Treatment phase: Participants will be instructed to use the device for the treatment of 4 qualifying migraine attacks (see below) as soon as possible and always within 60 minutes of onset during a period of up to 8 weeks. Participants will be instructed to use the device with the intensity level identified during the device training visit (with a range of ±5 units) and make sure the stimulation is perceptible but not painful. Participants will be instructed to avoid taking rescue medications within 2 hours post-treatment. If medications are used, participants will be instructed to record in the app when and which medication was taken. The participants will use the app to record pain intensity levels (none, mild, moderate, or severe) at baseline, 2- and 24-hours post-treatment, and to record the presence/absence of associated migraine symptoms (nausea, photophobia,

Nerivio TCH-004 Clinical Study Protocol (NCT04089761)

Doc ID: TEC0105

Revision #: 1.0

Page: 30 of 49

phonophobia) at baseline and 2 hours post-treatment. To assess functional disability, participants will also record at baseline, 2- and 24-hours post-treatment their response to the following question in their diary: "How do you rate your ability to do school-work or perform your usual activities?" using a 4-point scale ('as usual', 'some ability', 'a little ability', 'no ability at all'). At the beginning of each treatment, participants will also be asked to report the time elapsed from attack onset. Adverse events will be reported throughout this phase of the study.

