7.2.3. Exploratory endpoints

Exploratory efficacy endpoints include:

- Proportion of subjects achieving, for the test treatment, pain relief at 2 hours post treatment without use of rescue medication and no relapse of headache pain within 24 hours.
- Proportion of subjects achieving, for the test treatment, pain freedom at 2 hours post treatment without use of rescue medication and no relapse of headache pain within 24 hours.
- Proportion of subjects achieving, for the test treatment, improvement of at least one grade in functional disability at 2 hours post treatment without use of rescue medication.
- Proportion of subjects achieving, for the test treatment, improvement of at least one grade in functional disability at 24 hours post treatment without use of rescue medication.

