7.4. Analysis sets

Intent to treat analysis set (ITT)

The ITT analysis set includes all patients undergoing the treatment phase.

Modified intend to treat analysis set (mITT)

The mITT analysis set includes all patients undergoing the treatment phase and treat a test treatment within 60 minutes of attack onset. Subjects with no valid post baseline assessment will not be included in the relevant analysis.

Per-protocol analysis set (PP)

The PP analysis set includes all patients from the mITT analysis set without major protocol deviations. Main protocol instructions include:

- has started within 60 minutes of attack onset
- was administered to treat a qualifying migraine attack
- was administered for at least 30 minutes
- includes data on pain intensity at 2 hours post-treatment
- rescue medication was not used before or within 2 hours post-treatment

Nerivio TCH-004 Clinical Study Protocol (NCT04089761)

Doc ID: TEC0105

Revision #: 1.0

Page: 36 of 49

Statistical analysis of the analysis sets

The ITT analysis set will serve as the main set for safety assessments.

The mITT analysis set will serve as the primary set for the efficacy assessment.

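### The one-grade functional disability endpoints set no condition on the baseline grade, so participants rated 'as usual' at baseline cannot respond and the tabulated rate is capped

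*Combined protocol and SAP*

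**What the plan says.** Section 6.3 has participants rate their ability to do school work or usual activities at baseline, 2 hours and 24 hours on four grades: "as usual', 'some ability', 'a little ability', 'no ability at all".

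Section 6.4.3 counts as the 2-hour endpoint "The proportion of participants who achieve improvement of at least one grade in functional disability in the test treatment at 2 hours post-treatment", with no rescue medication. Section 7.2.3 repeats the rule for 2 hours and also asks for "improvement of at least one grade in functional disability at 24 hours post treatment without use of rescue medication". Neither section mentions the grade at which a participant starts.

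Three other parts of the plan bear on who enters the calculation:

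- **Timing and severity (Section 6.3).** Participants treat "as soon as possible and always within 60 minutes of onset", and the training instructions let treatment begin at headache or aura. They add: "Treatments of mild headaches are accepted". The definition of a qualifying attack has no minimum pain or disability.
- **Analysis set (Section 7.4).** Efficacy is assessed in the mITT set, which requires a test treatment within 60 minutes of onset. The only further exclusion is: "Subjects with no valid post baseline assessment will not be included in the relevant analysis".
- **Presentation (Section 7.5.4).** Each efficacy outcome is tabulated as a percentage with an exact two-sided 95% confidence interval. Logistic regression with baseline value and site as covariates is planned in addition.

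**The concern.** The responder rule needs room to improve, and one of the four baseline grades leaves none. A participant who begins at 'as usual' and remains there at 2 and 24 hours has the best outcome the scale can record, yet fails the stated rule. Nothing in Sections 6.4.3, 7.2.3, 7.4, 7.5.4 or 7.5.6 removes such participants from the denominator or says how they are classified.

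The other efficacy endpoints do name a starting state. Section 6.4.2 lists the pain grades from which relief or freedom is reached, and its symptom endpoints refer to the symptom being reported at baseline. Only the functional endpoints are silent on this.

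What is at stake is how a descriptive percentage is read. The study has one arm, so no control group shares the ceiling, and the tabulated percentage is the result. If the denominator stays open, the same data can yield two quite different percentages, and the choice could be made after the data are seen.

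**Working it through.** **Plan's own figure.** There is none to reproduce. The documents state no expected rate, sample size or power for functional disability.

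**Inputs**

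- Scale, responder rule and analysis set: Sections 6.3, 6.4.3, 7.2.3 and 7.4.
- q, the share rated 'as usual' at baseline of the test treatment: not given. Assumed range 5% to 50%.
- r, the one-grade response rate among participants below 'as usual' at baseline: not given. Assumed 60%, with 50% and 70% alongside.
- n = 110, from Section 7.3. It was set for pain relief and is used here only to show interval widths.

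**Formula.** Participants at 'as usual' contribute no responders, so the rate over all analysed participants is (1 - q) × r, with maximum 1 - q.

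| q | Maximum | r = 50% | r = 60% | r = 70% |
|---|---|---|---|---|
| 5% | 95% | 47.5% | 57% | 66.5% |
| 10% | 90% | 45% | 54% | 63% |
| 20% | 80% | 40% | 48% | 56% |
| 35% | 65% | 32.5% | 39% | 45.5% |
| 50% | 50% | 25% | 30% | 35% |

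For example, at q = 20% and r = 60%: 0.80 × 0.60 = 48%. With the denominator limited to those able to improve, the r = 60% column would read 60% in every row.

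**Same responders, two denominators** (n = 110, r = 60%, exact 95% intervals)

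- q = 10%: 110 × 0.90 = 99 can improve, and 99 × 0.60 ≈ 59 respond. 59/110 = 53.6% (43.9 to 63.2) against 59/99 = 59.6% (49.3 to 69.3).
- q = 35.4%: 110 × 0.646 ≈ 71 can improve, and 71 × 0.60 ≈ 43 respond. 43/110 = 39.1% (29.9 to 48.9) against 43/71 = 60.6% (48.3 to 72.0).

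The 35.4% is the share of active-group test treatments with mild baseline pain in the adult pivotal study (35/99, Section 4.2.2, Table 4). It measures pain in adults, not function in adolescents, and serves only as an illustration.

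**Effect of treatment timing.** Suppose earlier treatment raised q from 10% to 35.4%.

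- With r fixed at 60%, the rate falls from 0.90 × 0.60 = 54% to 0.646 × 0.60 = 39%.
- If r also rose from 50% to 80%, the rate would rise from 0.90 × 0.50 = 45% to 0.646 × 0.80 = 52%.
- Break-even is a rise in r by a factor of 0.90/0.646 = 1.39.

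The direction therefore depends on two quantities that the documents do not give.

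**Does the planned model help?** It does not change the tabulated percentage. If baseline grade is entered as a category, the 'as usual' stratum can contain no responders, and the logistic fit will show separation there.

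**The case against.** The strongest reply is that the proportion of all treated participants who improve is a legitimate and conservative quantity. In an uncontrolled study it understates benefit, and limiting the denominator answers a different question with fewer participants. That stands as far as it goes: for any q above zero the all-participant rate lies below the rate among those able to improve, and calling it biased presumes the second target. It does not answer the literal scoring of sustained full function as failure, nor the absence of a stated denominator.

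The size may also be small. Mild pain is not full function, and a participant with mild pain and photophobia could well choose 'some ability'. At q = 5% an assumed 60% becomes 57%. That stands, and it is why the range starts low.

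Nothing is lost in data collection, since the grade is recorded at all three times. Section 9.1 also lists a statistical analysis plan kept separately from the protocol, where a convention could sit. That too stands, but the statistical section under review contains none.

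A reader might go further and infer that the early-treatment instruction lowers the response rate, that many participants will start at 'as usual', or that the endpoint reflects treatment delay as much as effect. The documents support none of these. They give no baseline distribution of disability and no link between delay and disability, and the mITT set already limits delay to 60 minutes. A claim that rates cannot be compared across sites would also go too far. The poolability assessment in Section 7.5.5 is optional and does not name this endpoint, and the planned models adjust for baseline value and site.

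**Conclusion.** The point holds as a defect of definition. The rule gives participants rated 'as usual' at baseline no way to respond, no text excludes or classifies them, and the tabulated rate at 2 and at 24 hours is capped at 1 - q. The cap follows from the scale and the rule alone. Its size rests on two assumptions, q and r: at r = 60% the shortfall runs from 3 percentage points at q = 5% to 30 points at q = 50%. The denominator is best described as unspecified, with the mITT set of Section 7.4 as the default reading.

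Severity is minor. These are two exploratory endpoints with no test, success criterion or decision attached, in a study whose primary endpoints are safety and tolerability.

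**What to change.** In Sections 6.4.3 and 7.2.3:

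1. Compute the one-grade improvement endpoints at 2 and 24 hours among participants rated 'some ability' or worse at baseline of the test treatment, and state that number with each percentage.
2. Report the distribution of baseline grades for the test treatment.
3. Add, for all mITT participants with data, the proportion rated 'as usual' at 2 hours and at 24 hours without rescue medication. This keeps those who began at full function in view.

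The cost is a few sentences of endpoint wording and a few table lines, all from data already collected. The downside is a smaller denominator and a wider interval for the one-grade endpoints. In the q = 35.4% illustration the exact interval widens from 19.0 points (29.9 to 48.9) to 23.7 points (48.3 to 72.0).

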6.5. Methods and timing of assessing and analysing variables

Once the last patient will complete the treatment phase of the study and all the queries will be resolved, the database will be locked, cleaned and exported for final statistical analysis. A study report will be issued following the final database lock.

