6.3. Procedures

This open label study includes 3 phases and up to 4 visits. All visits will be conducted in the presence of a parent/guardian.

First visit – enrollment: The first visit will include screening, enrollment and training on the application in diary mode. The screening process will include an eligibility assessment and a urine pregnancy test. Following successful screening, enrollment interview and signing an informed consent by the parent/guardian and an informed assent by the participant. The participants will be trained to use the electronic diary application, installed on their own smartphones. The site personnel will be required to document the training session in the CRF. During this visit, participants will complete baseline questionnaires that included information on the frequency and severity of their migraine attacks, typical associated symptoms, use of preventive and acute treatments, and the effect that their migraine attacks have on their daily routine and quality of life.

Nerivio TCH-004 Clinical Study Protocol (NCT04089761)

Doc ID: TEC0105

Revision #: 1.0

Page: 29 of 49

Phase 1 – run-in phase: After the enrollment visit, participants will undergo a 4-week migraine diary phase aimed to collect baseline migraine characteristics and further assess eligibility. Participants will be asked to report in the application each migraine attack. These reports will be transferred by the application to the electronic data collection (EDC) system, where they will be collected and registered. Participants who did not have at least 3 migraine attacks will be excluded from the study. Eligibility will also be determined based on the compliance of participants to report the attacks within one hour from attack onset and report the pain level at 2 hours post-treatment in at least 66.7% of the reported attacks.

Second visit – **Device training visit:** Eligible participants who meet the run-in requirements will receive the Nerivio[™] device. The device will be registered and connected by Bluetooth to their smartphone. During this visit, participants and their parent/guardian will be trained to use the device, including finding the optimal individual stimulation intensity level (perceptible but not painful). The site will also carefully review with the patient and parent/caregiver how to identify a qualifying migraine attack (see below) and provide detailed instructions on study procedures.

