Participants who do not achieve satisfactory relief at 2 hours post-treatment may treat again with the Nerivio[™] device or may treat with usual care at that time or any time thereafter if the headache does not resolve. Participants will also be able to treat headache recurrence with the device. Attacks that are not treated with the device may be treated with usual care.

The first reported treatment will be considered a "training" treatment, aimed to verify that the participants use the device properly, and will only be included in the safety analysis. The efficacy evaluation will be performed on the first treatment of a qualifying attack (see below) following the training treatment (hereby termed "test treatment").

Qualifying migraine attack

A qualifying migraine attack is defined as a migraine attack that:

- 1. Was not preceded by another migraine or other headache within the preceding 24 hours
- 2. Was not preceded by the use of specific or non-specific acute migraine medications within the previous 24 hours
- Occurred in a setting in which the patient could properly administer the treatment (that is, it is possible to initiate a complete treatment within 60 minutes of onset and the participant will be able to complete the migraine diary at 2 hours after treatment)

Third visit – Termination of the treatment phase and free-use phase initiation: Following the 8-week period of the treatment phase, participants will return to the clinic to return the device and fill questionnaires assessing satisfaction and user experience. All participants who complete the treatment phase will be offered to participate in an additional 8-week phase in which the device can be incorporate into usual care.

Phase 3 – Free-use phase: Participants will continue in an 8-week phase in which they will be able to use the device according to their preferences for the treatment of their migraine attacks.

Fourth (final) visit – End of study: Participants will return to the clinic following the end of the 8-week free-use phase, at which time they will return the device.

Nerivio TCH-004 Clinical Study Protocol (NCT04089761)

Doc ID: TEC0105

Revision #: 1.0 Page: 31 of 49

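### The final database lock falls at the end of the treatment phase, but the primary tolerability endpoint runs to the end of the study, so follow-up for both primary safety endpoints varies with enrolment date

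*Combined protocol and SAP*

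**What the plan says.** Section 6.5 ties the lock to the last participant finishing the treatment phase: "Once the last patient will complete the treatment phase of the study and all the queries will be resolved, the database will be locked". The data are then "cleaned and exported for final statistical analysis", so this is not described as an interim cut. The same section adds: "A study report will be issued following the final database lock". No second lock is described.

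Section 6.3 sets out a longer study: "This open label study includes 3 phases and up to 4 visits". Of the third phase it says: "Participants will continue in an 8-week phase in which they will be able to use the device". A fourth visit, labelled as the end of the study, follows that phase. Section 6.3.1 counts the free-use weeks in each continuing participant's study duration.

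Section 6.4.1 gives two primary endpoints. The first is adverse-event incidence, with no time window. The second is "The percent of subjects who fail to complete the study because of adverse events", and Section 7.5.3 repeats it. Neither is restricted to the treatment phase.

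On adverse-event collection, the treatment-phase text in Section 6.3 says: "Adverse events will be reported throughout this phase of the study". The free-use text is silent. Section 12.2 requires every adverse event to be recorded, without limiting this to a phase, and provides follow-up for device-related events still ongoing at the last visit.

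**The concern.** The lock rule and the tolerability endpoint refer to different ends of the study. Someone who continues into free use has not completed the study until the fourth visit. At the Section 6.5 lock, some continuing participants will still be using the device, and it cannot yet be known whether they will complete or will leave because of an adverse event. Counting them as completers would assume the favourable answer.

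Adverse-event incidence has a related problem. A participant who finished the treatment phase well before the lock contributes all of free use, and one who finished last contributes little or none. A single percentage would then mix different lengths of follow-up, set by enrolment date.

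This matters because safety and tolerability are the primary endpoints, the participants are minors, and Section 3.1 states that the study is meant to support a wider indication. Free use is also the phase in which participants choose when to use the device, so it is the nearest the study comes to ordinary use.

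**Working it through.** **Timeline.** Section 6.3 gives the run-in length ("participants will undergo a 4-week migraine diary phase"), a treatment phase of up to 8 weeks and a free-use phase of 8 weeks.

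- Run-in plus treatment: 4 + 8 = 12 weeks. This reproduces the figure in Section 6.3.1.
- With free use: 12 + 8 = 20 weeks. The fourth visit therefore comes about 8 weeks after the event that triggers the lock.

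**Status at the lock.** Let s be the weeks between a participant's own end of treatment phase and that of the last participant, and let L be the weeks from the latter to the lock. Free-use weeks captured are min(8, s + L).

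- Last participant, immediate lock: min(8, 0 + 0) = 0 of 8 weeks.
- Last participant, 4-week delay: min(8, 0 + 4) = 4 of 8 weeks.
- A participant who finished at least 8 weeks before the lock: all 8 weeks.

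**Average loss.** The documents give no accrual period, lock delay or free-use uptake, so these are assumptions. Suppose everyone uses the full 8-week treatment phase and then enters free use, free-use events are recorded, and entry to the treatment phase is uniform over A weeks. For A of at least 8 − L:

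- share of free-use time missed = (8 − L)² / (2 × 8 × A)
- share of participants cut off before week 8 of free use = (8 − L) / A

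With L = 0 the first formula becomes 4/A, and with L = 4 it becomes 1/A. For simultaneous entry the missed share is (8 − L)/8 and everyone is cut off.

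| Entry period A | Time missed, L = 0 | Participants cut off, L = 0 | Time missed, L = 4 | Participants cut off, L = 4 |
|---|---|---|---|---|
| Simultaneous | 100% | 100% | 50% | 100% |
| 8 weeks | 50% | 100% | 12.5% | 50% |
| 12 weeks | 33% | 67% | 8% | 33% |
| 26 weeks | 15% | 31% | 4% | 15% |
| 52 weeks | 8% | 15% | 2% | 8% |

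If only some participants continue, and continuing is unrelated to entry date, these shares still apply to those who do. The total time lost shrinks in proportion to uptake.

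**Endpoints not touched.** The efficacy endpoints rest on the test treatment, which falls in the treatment phase, and their last assessment is at 24 hours. The lock does not affect them or the sample size.

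**The case against.** The strongest reply is that analysing the main phase when it ends and reporting an optional extension separately is an ordinary design. Sections 7.4 and 7.5.1 base the safety analysis on those who entered the treatment phase, and the sponsor may have meant the same window for the endpoints. That would be coherent, but it is not written. The analysis set fixes who is counted, not for how long, and the tolerability endpoint refers to the study.

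Section 6.5 speaks of a final lock, Section 6.6 mentions interim as well as final analyses, and Section 9.1 refers to a separate analysis plan. A later lock may be described elsewhere. These sections do not define one, and Section 6.5 attaches the final analysis to the end of the treatment phase. Because the lock waits for queries to be resolved, an immediate lock is the extreme case. That point stands, and it is why a range is shown.

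The Kaplan-Meier analysis in Section 7.5.3 could censor participants still in free use. No censoring rule is given, however, and the primary endpoint is a simple percentage.

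Three stronger readings are tempting, and the documents do not support them:

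- **A reader might infer that adverse events are collected only in the treatment phase.** Section 12 defines them by their timing relative to device use, and Section 12.2 records all of them and follows device-related ones from the last visit. Section 6.3 leaves a gap in wording but does not stop collection.
- **A reader might infer that half of the device exposure is lost, because free use is 8 of 16 device weeks.** That is calendar time. Exposure to this device is a number of treatments: four attacks are requested in the treatment phase, and none is specified in free use.
- **A reader might infer that incidence would nearly double, by applying the adult device-related rate of 4.8% once to each phase.** That rate comes from a phase of 4 to 6 weeks, and the step assumes independence between phases in the same people. In the adult pivotal trial (Section 4.2.2), 14 device-related events fell in 6 of 126 active participants. Scattered at random they would have reached about 126 × (1 − (125/126)^14) = 13.3 people, so events cluster within people. Participants who cannot tolerate stimulation may also be withdrawn before free use begins.

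**Conclusion.** The point holds as a conflict between a stated lock rule and a primary endpoint. Followed as written, Section 6.5 closes the data before the tolerability outcome is known for participants still in free use. It also leaves follow-up for both primary safety endpoints dependent on enrolment date. The first consequence needs only that someone is in free use at the lock. The second also needs free-use events to be recorded, as Section 12.2 implies.

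The size is uncertain. If everyone continues, between 100% and about 8% of free-use time is missed with an immediate lock, and between 50% and about 2% with a 4-week delay. Slow accrual and a delayed lock could make the loss small. The mismatch in definition would remain even then, so it should be corrected.

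**What to change.** - **Section 6.5:** keep the end-of-treatment-phase lock for efficacy and for the treatment-phase safety analysis. Add a final safety lock after the last participant's fourth visit.
- **Section 6.3:** state that the adverse-event recording in Section 12.2 applies through free use and at the fourth visit.
- **Sections 6.4.1 and 7.5.3:** report both primary safety endpoints twice. The first report covers the treatment phase, with the same window for every participant. The second covers the whole study, with the number of treatments and the time at risk.

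The cost is protocol wording and a second lock. The complete safety report would come about 8 weeks later, plus about 2 weeks where device-related events ongoing at the last visit are followed under Section 12.2. The sample size and the timing of the efficacy results do not change.
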